6 STUDY OBJECTIVES AND ENDPOINTS

6.1 Objectives

The objective of the study is to evaluate the safety of bilateral, sequential sub-retinal administration of a single dose of AAV2-REP1 in adult male subjects with CHM.

6.2 Endpoints

The safety of bilateral administration of AAV2-REP1 will be evaluated with the following safety measures:

- BCVA as measured by the Early Treatment of Diabetic Retinopathy Study (ETDRS) chart
- Ophthalmic examination assessments (including intraocular pressure [IOP], slit lamp examination, lens opacity grading and dilated ophthalmoscopy)
- Spectral domain optical coherence tomography (SD-OCT)
- Fundus autofluorescence (AF)
- Fundus photography
- Microperimetry
- AE reporting
- Vector shedding post-treatment
- Immunogenicity sampling post-treatment
- Vital signs

The following will also be considered secondary efficacy endpoints:

- Change from Baseline in BCVA as measured by the ETDRS chart
- Change from Baseline in AF
- Change from Baseline in SD-OCT
- Change from Baseline in microperimetry

7 INVESTIGATIONAL PLAN

7.1 Overall Study Design

This is a multi-centre, open-label, prospective, 2-period, bilateral interventional safety study of AAV2-REP1 in adult male subjects with genetically confirmed CHM. The study will consist of a Screening Period followed by 2 treatment periods (Period 1 and Period 2) with up to 9 visits per treatment period. A second baseline visit prior to surgery of SE2 (Period 2, Visit 1) may be required. A study schematic is presented in **Figure 1**.

Figure 1 Overall Study Schematic

During the Screening Period, subjects will be assessed for eligibility of both eyes. The Investigator will assign the order in which the eyes are treated (i.e., study eye 1 [SE1]-Period 1 and study eye 2 [SE2]-Period 2, respectively) with a number assigned to each eye. This will be done in collaboration with the subject; however, the worse eye will generally be selected for first treatment. Study eye selection and eligibility for surgery will then be confirmed collectively by the Patient Eligibility Review Committee, which includes the Investigator, a consulting surgeon, and the Sponsor (see the Patient Eligibility Review Plan). The estimated target interval between the surgical procedures of SE1 and SE2 will be determined at the Screening Visit.

Each study eye will be followed for at least 12 months post-treatment, for up to 9 visits per treatment period: Visit 1 (Day 0, Injection Day Visit); Visit 2 (Day 1, post-operative follow-up visit); Visit 3 (Day 3 + 2 Days); Visit 4 (Day 7 -1/+2 Days); Visit 5 (Day 14 ± 3 Days); Visit 6 (Month 1 ± 7 Days); Visit 7 (Month 3 ± 14 Days); Visit 8 (Month 6 ± 14 Days) and Visit 9 (Month 12 ± 14 Days; end of study visit).

At Period 1, Visit 1 (Day 0, Injection Day Visit for SE1), subjects will undergo a vitrectomy with retinal detachment and receive a sub-retinal injection of AAV2-REP1 in SE1. Visits 2-9 will then be conducted according to the Schedule of Study Procedures, unless Period 2 commences during the time of follow-up for SE; in which case, the study visits will continue following the schedule for SE2. Ophthalmic assessments during Period 1, Visits 2-9 will be performed on both eyes.

The interval between SE1 and SE2 treatment is expected to vary among subjects from weeks to many months. While the interval will be decided on a case-by-case basis, an effort will be made to schedule varying treatment intervals in order to better characterise the immunological and safety profile of sequential treatment administration. Thus, approximately 20 subjects each will be treated with a short- (<6 month), medium- (6-12 months), or long- (>12 month) surgery window between treatment of the first and second

eye. Because the timing of the second surgery visit (Period 2, Visit 1) will vary among subjects, the duration of study Period 1 will also be variable.

The post-operative outcome and visual function of SE1 will inform the scheduling of Period 2. Signs of post-operative inflammation or other post-operative sequelae, as judged by the Investigator, should be resolved in SE1 for the subject to continue to Period 2. After comprehensive evaluation of all safety assessments and visual functional tests of SE1 and SE2, the Investigator will determine the eligibility of the subject and decide the appropriate time to schedule SE2, Visit 1.

All baseline ophthalmic assessments must be conducted within 10 weeks prior to SE2 surgery (Period 2, Visit 1). If these assessments are not available within the required timeframe, a Baseline Visit must be added to collect current baseline data on SE2. Study eye selection and eligibility for surgery will then be confirmed collectively by the Patient Eligibility Review Committee, which includes the Investigator, a consulting surgeon, and the Sponsor (see the Patient Eligibility Review Plan). If, at that time, BCVA in SE2 is <34 ETDRS letters, surgery may be performed when, in the opinion of the Patient Eligibility Review Committee: 1) the subject is found eligible by all other inclusion and exclusion criteria, and 2) the subject is considered an appropriate candidate who has potentially modifiable disease.

At Period 2, Visit 1 (Day 0, Injection Day Visit for SE2) subjects will undergo a vitrectomy with retinal detachment and sub-retinal injection of AAV2-REP1 in the contralateral, untreated eye (SE2). Post-treatment, subjects will no longer follow the Period 1 visit schedule, but will instead attend Period 2, Visits 2-9 according to the Schedule of Study Procedures. Ophthalmic assessments scheduled for Period 2, Visits 2-9 will be performed on both eyes.

Study data will thus be collected for both eyes. Subjects will be assessed for safety and efficacy throughout the study, as outlined in the Schedule of Study Procedures ([Table 1](#)). The safety evaluation will be based on a full ophthalmic examination (indirect ophthalmoscopy, slit lamp examination, IOP, anterior chamber and vitreous inflammation grading and lens opacities classification system [LOCS] III cataract grading); fundus photography; AE reporting; vector shedding and immunogenicity assessment and vital signs. The efficacy evaluation will be based on BCVA (as measured by the ETDRS chart), AF, SD-OCT and microperimetry. Any safety information collected as a result of the efficacy assessments (e.g., BCVA) will also be used in the overall safety evaluation, as applicable.

Subjects who develop cataracts may undergo cataract surgery if deemed clinically necessary. If cataract surgery is performed, it should be carried out at least 4 weeks before Month 12 (Visit 9) for the respective eye. The cataract surgery timing must be discussed with the medical monitor prior to the procedure.

A subject is considered to have completed the study if he completes Period 2, Visit 9 (Month 12). The end of the trial is the date the last subject completes Period 2, Visit 9 (Month 12) assessments (or early termination [ET] assessments in the event of premature discontinuation) or the date of last data collection if the last subject is lost to follow-up. After study completion, subjects will be invited to participate in a long-term safety follow-up study that will permit continued safety and efficacy monitoring over an extended period of time post-treatment.

Subjects Previously Treated with AAV2-REP1

Subjects who have previously participated in a clinical trial of AAV2-REP1 for the treatment of CHM and have received AAV2-REP1 in one eye may be eligible for participation in this study. In these cases, only the subject's untreated eye will be assessed for eligibility per [Section 8](#). Following the Screening Visit and determination of eligibility, the subject will move directly into Period 2 for treatment of SE2.

For subjects who received previous treatment with AAV2-REP1, biological samples must be available to obtain an adequate immunology profile related to treatment of the first eye in the previous study. These subjects will require Sponsor approval before being enrolled into the study.

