The interval between SE1 and SE2 treatment is expected to vary among subjects from weeks to many months. While the interval will be decided on a case-by-case basis, an effort will be made to schedule varying treatment intervals in order to better characterise the immunological and safety profile of sequential treatment administration. Thus, approximately 20 subjects each will be treated with a short (<6 month), medium (6-12 months), or long (>12 month) surgery window between treatment of the first and second eye. Because the timing of the second surgery visit (Period 2, Visit 1) will vary among subjects, the duration of study Period 1 will also be variable. The post-operative outcome and visual function of SE1 will inform the scheduling of Period 2. Signs of post-operative inflammation, or other post-operative sequelae, as judged by the Investigator, should be resolved in SE1 for the subject to continue to Period 2. After comprehensive evaluation of all safety assessments and visual functional tests of SE1 and SE2, the Investigator will determine the eligibility of the subject and decide the appropriate time to schedule SE2, Visit 1.

All baseline ophthalmic assessments must be conducted within 10 weeks prior to SE2 surgery (Period 2, Visit 1). Eligibility for SE2 surgery will then be confirmed collectively by the Patient Eligibility Review Committee, which includes the Investigator, a consulting surgeon, and the Sponsor (see the Patient Eligibility Review Plan). If, at that time, the BCVA in SE2 is <34 ETDRS letters, surgery may be performed when, in the opinion of the Patient Eligibility Review Committee: 1) the subject is found eligible by all other inclusion and exclusion criteria, and 2) the subject is considered an appropriate candidate who has potentially modifiable disease.

At Period 2, Visit 1 (Day 0, Injection Day Visit for SE2), subjects will undergo a vitrectomy with retinal detachment and sub-retinal injection of AAV2-REP1 in the contralateral, untreated eye (SE2). Post-treatment, subjects will no longer follow the Period 1 visit schedule, but will instead attend Period 2, Visits 2-9 according to the Schedule of Study Procedures. Ophthalmic assessments scheduled for Period 2, Visits 2-9 will be performed on both eyes.

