10.1.1 Baseline Visit, Period 2 (<10 Weeks from Visit 1, Period 2 [SE2])

The following baseline assessments for Period 2 must be performed within 10 weeks prior to surgery for SE2 (Visit 1, Period 2). If the assessments have not been performed within a regularly scheduled visit within this window, an additional visit is required.

- Vital signs
- Weight
- Vector shedding sampling – blood, tears (both eyes), urine, saliva
- Immunogenicity sampling
- BCVA
- Microperimetry

- Full ophthalmic examination, including IOP, a slit-lamp examination, lens opacity, and dilated fundus examination
- SD-OCT
- AF
- 7-field colour fundus photography (including stereo photographs for fields 1, 2, and 3)
- AE and SAE monitoring
- Concomitant medication, procedures and treatment review

Eligibility for SE2 surgery will then be confirmed collectively by the Patient Eligibility Review Committee, which includes the Investigator, a consulting surgeon, and the Sponsor (see the Patient Eligibility Review Plan).

If BCVA in SE2 is <34 ETDRS letters, surgery may be performed when, in the opinion of the Patient Eligibility Review Committee:

1. the subject is found eligible by all other inclusion and exclusion criteria, and
2. the subject is considered an appropriate candidate who has potentially modifiable disease.

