16 APPENDIX

Table 1 presents a schedule of study procedures.

Table 1: Schedule of Study Procedures

Visit	Period 1 Screening ^a	Period 2 Baseline ^b (<10 Weeks from Visit 1, Period 2)	Study Period 1 / Period 2									ET Visit ^d	Unscheduled Visit ^e
			V1	V2	V3	V4	V5	V6	V7	V8	V9		
Study Day/Month Visit Window			Day 0 Injection Day ^c (≤10 weeks Screening)	Day 1 Post op	Day 3 +2 d	Day 7 - 1/+2 d	Day 14 ± 3d	M 1 ± 7d	M 3 ± 14d	M6 ± 14d	M 12 ± 14d		
Assessment/Procedures (All subjects/eyes)													
Informed Consent	X												
Demography, medical and ocular history	X												
Vital signs (pulse, blood pressure)	X	X		X	X						X	X	
Weight ^f	X	X											
Vector shedding sampling ^g	X	X		X	X	X	X	X			X ^h		
Immunogenicity sampling ⁱ	X	X		X		X	X	X	X	X	X	X	
BCVA	X	X		X	X	X	X	X	X	X	X	X	X
Microperimetry	X	X						X	X	X	X	X	
Full ophthalmic exam ^j	X	X	X	X	X	X	X	X	X	X	X	X	X
SD-OCT	X	X		X		X	X	X	X	X	X	X	X
Autofluorescence	X	X				X	X	X	X	X	X	X	
7-field colour fundus photos ^k	X	X									X	X	
Study drug / sub-retinal injection / vitrectomy / retinal detachment			X										
AE/SAE monitoring ^l	X	X	X	X	X	X	X	X	X	X	X	X	X

Visit	Period 1 Screening ^a	Period 2 Baseline ^b (<10 Weeks from Visit 1, Period 2)	Study Period 1 / Period 2									ET Visit ^d	Unscheduled Visit ^e
			V1	V2	V3	V4	V5	V6	V7	V8	V9		
Study Day/Month Visit Window			Day 0 Injection Day ^c (≤10 weeks Screening)	Day 1 Post op	Day 3 +2 d	Day 7 - 1/+2 d	Day 14 ± 3d	M 1 ± 7d	M 3 ± 14d	M6 ± 14d	M 12 ± 14d		
Assessment/Procedures (All subjects/eyes)													
Concomitant medication, procedures, and treatment review ^m	X	X	X	X	X	X	X	X	X	X	X	X	X

Abbreviations: AE=adverse event; BCVA=best corrected visual acuity; ET=early termination; IOP=intraocular pressure; LOCS=lens opacities classification system; SAE=serious adverse event; SD-OCT=spectral domain optical coherence tomography; SE1=Study Eye 1; SE2=Study Eye 2

^a Screening Visit/Period must be performed ≤10 weeks of Period 1, Visit 1. Selection of SE1 and SE2 will be determined by the Investigator in collaboration with the subject.

^b Baseline assessments must occur before the SE2 is dosed. These can occur at a regularly scheduled visit if that visit is within 10 weeks prior to surgery in SE2. If it has been more than 10 weeks since a visit, the subject must return for assessments at this Baseline Period 2 visit.

^c Subjects will undergo vitrectomy and AAV2-REP1 administration to SE1 in Period 1; SE2 in Period 2.

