^d ET visit is to be performed if a subject discontinues at any time.

^e If clinically indicated, subjects may need to return to the site for an unscheduled visit. At a minimum, the following assessments will be performed: BCVA, full ophthalmic examination, SD-OCT, AF, concomitant medication, procedures, and treatment review and AE/SAE monitoring.

^f Weight is collected for dose calculation of the corticosteroid regimen.

^g Blood, tears (both eyes), urine and saliva samples.

^h If ET visit occurs within 3 months post-treatment.

ⁱ Immunoassays are planned to assess cell-based and antibody-based immune responses against AAV2-REP1. Enzyme-linked immunospot (ELISPOT) assays will be used for the assessment of T-cell-mediated immune responses to transgene product (REP1) and the capsid. Antibody responses against the capsid and transgene product will be measured using a cell-based neutralization assay and an enzyme-linked immunosorbent assay (ELISA), respectively. All immunogenicity samples will be sent to a central laboratory for analysis.

^j The ophthalmic examination will include IOP, slit lamp examination, lens opacity grading, and dilated ophthalmoscopy. The same slit lamp machine and lighting conditions should be used across the study for each subject.

^k Stereo photos for fields 1, 2, 3.

^l AEs/SAEs will be collected from the time the subject provides written informed consent (Screening Visit) through Period 2, Visit 9 (or ET Visit, if applicable).

^m Subjects will be given a course of oral corticosteroid before each surgical visit, and instructed to start taking the drug 2 days prior to SE1/SE2 treatment, unless the SE2 surgical treatment coincides with the SE1 steroid treatment period, when an extended course of steroid can cover both surgical treatments. This regimen is outlined in detail in [Section 9.8](#).

For SE1, the Full Corticosteroid Regimen should be initiated as described. For SE2, and surgeries that occur on day 21 or later, the Full Corticosteroid Regimen should be initiated as described, beginning 2 days before the scheduled SE2 surgery. If SE2 is to be performed prior to Study Day 21, then the Full Corticosteroid Regimen should be initiated 2 days prior to the scheduled surgery for SE2, and this will supersede the steroid taper in progress for SE1. The full 21 days of treatment will then be completed for SE2.

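### Protocol 7.1, 10.1.1 and Table 1 footnote b set different conditions for adding the Period 2 Baseline Visit, so items that 10.1.1 wants current can be out of date at second-eye surgery

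*Protocol*

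**What the plan says.** Three places in the current protocol govern the same step before SE2 surgery.

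- **Section 7.1** sets a 10-week limit on baseline ophthalmic assessments and then says: "If these assessments are not available within the required timeframe, a Baseline Visit must be added to collect current baseline data on SE2".
- **Section 10.1.1** makes a longer list mandatory within 10 weeks of SE2 surgery: vital signs, weight, vector shedding and immunogenicity samples as well as the ophthalmic tests and fundus photographs. It continues: "If the assessments have not been performed within a regularly scheduled visit within this window, an additional visit is required".
- **Table 1, footnote b** has three sentences. It opens with a general duty: "Baseline assessments must occur before the SE2 is dosed". The middle sentence allows a routine visit to serve this purpose, provided it falls inside the 10-week window. The last one says when a subject has to be called back: "If it has been more than 10 weeks since a visit, the subject must return for assessments at this Baseline Period 2 visit".

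The synopsis repeats the 10-week ophthalmic requirement but says nothing about adding a visit. Table 1 footnote f gives the reason for one of the listed items: "Weight is collected for dose calculation of the corticosteroid regimen". Protocol 13.4 and SAP 4.3 take as baseline the latest available value before treatment in the period, with no limit on its age. Only the immunogenicity baseline has a 10-week limit (SAP 4.17.11.1).

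**The concern.** The three conditions turn on different things: ophthalmic items in 7.1, every listed item in 10.1.1, and elapsed time since a visit in the last sentence of footnote b. The regular visits do not collect everything on the 10.1.1 list. A site working from 7.1 or from the schedule table could therefore conclude that no extra visit is needed when 10.1.1 requires one. Section 10 sends the reader to Table 1 for the schedule, so footnote b is likely to be used.

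Two things are at stake. First, the baseline rule would accept an old value without comment. The SE2 fundus-photograph shift (SAP 4.17.8) could then include untreated progression between the old image and surgery, and the vital-sign change (SAP 4.17.13) could start from an old reading. In a single-arm safety study no control group would reveal this. Second, weight feeds the steroid calculation, and the passages do not agree on whether a current weight must exist before the second course.

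**Working it through.** **Inputs.** Sections 10.1 to 10.8 give the content of each visit. I place Visits 1-9 at nominal Days 0, 1, 3, 7, 14, 30, 91, 182 and 365 after first-eye surgery, and take 10 weeks as 70 days. Screening may be up to 10 weeks before first-eye surgery; Day -28 is my illustration, with Day -1 and Day -70 as the range.

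**Where the critical items are collected before SE2 surgery:**

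| Item | Screening | Visits 1-9 |
|---|---|---|
| Weight | yes | none |
| Fundus photographs | yes | Visit 9 only |
| Vital signs | yes | Visits 2, 3 and 9 |
| Vector shedding | yes | Visits 2-7; not Month 6 or Month 12 |

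**Rule.** An item collected on day d is current for surgery on day t if d < t ≤ d + 70.

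- Screening on Day -28: current to -28 + 70 = Day 42. From Day -1 it is current to Day 69; from Day -70, never for SE2 surgery.
- Vital signs: 3 + 70 = Day 73, then again Days 366-435 after Visit 9 (365 + 70 = 435).
- Shedding: 91 + 70 = Day 161.
- Any visit at all: continuously to Day 161, then Days 183-252 (182 + 70 = 252), then Days 366-435.

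**10.1.1 as the trigger.** With no weight at Visits 1-9, the extra visit is avoided only while Screening is current: to Day 42 here.

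**7.1 as the trigger.** Only Screening and Visit 9 carry the full ophthalmic set including photographs. The visit is avoided to Day 42 (nothing missing) and on Days 366-435. In the later range weight and shedding are out of date; vital signs are current because Visit 9 takes them.

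**Last sentence of footnote b as the trigger (Screening on Day -28):**

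| SE2 surgery day | Visit avoided? | 10.1.1 items out of date |
|---|---|---|
| 15-42 | yes | none |
| 43-73 | yes | weight, photographs |
| 74-161 | yes | weight, photographs, vital signs |
| 162-182 | no | - |
| 183-252 | yes | weight, photographs, vital signs, shedding |
| 253-365 | no | - |
| 366-435 | yes | weight, shedding |

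**Greatest ages at those edges.**

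- Photographs: 252 + 28 = 280 days (252 + 70 = 322 if Screening was on Day -70).
- Weight: 435 + 28 = 463 days (435 + 70 = 505).
- Vital signs: 252 - 3 = 249 days.
- Shedding: 252 - 91 = 161 days after Month 6, and 435 - 91 = 344 days after Month 12.

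**A case the protocol encourages.** Section 10.1 asks that SE2 surgery fall on a planned Period 1 visit. At Month 3 the Month 1 visit is 91 - 30 = 61 days old, so footnote b's last sentence asks for nothing more. Weight and photographs are then 91 + 28 = 119 days old and vital signs 91 - 3 = 88 days old; 10.1.1 would require a visit.

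**The case against.** The best reply is that there is no conflict of obligation. Section 10.1.1 is mandatory, nothing waives it, and a site that follows it satisfies all three passages. Footnote b, read whole, starts by requiring the baseline assessments before dosing and lets those assessments be done at a regular visit; it does not say that a visit without them will do. Nothing stops a site adding weight or photographs to a regular visit.

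Most of this stands. A reader might infer that footnote b authorises SE2 surgery without the listed items. Its first sentence rules that out. What remains is that its last sentence, and the condition in 7.1, tell a site when to call the subject back in terms that do not match the 10.1.1 list.

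The consequences are also limited. Shedding is tabulated by category with no change from baseline (SAP 4.17.12), immunogenicity has its own window, and fundus shift is descriptive. If SE2 surgery takes the Month 6 or Month 12 slot, the previous visit is 182 - 91 = 91 or 365 - 182 = 183 days earlier, so footnote b itself requires the Baseline Visit.

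Other stronger readings also fail:

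- Vital signs do not lapse under 7.1, because both visits that can meet it include them.
- The synopsis contains no trigger for a visit.
- It is not true that no scheduled visit can ever meet 10.1.1, since a recent Screening does.
- Footnote b avoids the visit on (161 - 14)/(182 - 14) = 88% of days in the short range, counted from Day 14. That is not a share of affected subjects: it counts calendar days and includes days on which nothing is out of date.
- No passage says that the second steroid calculation uses the Screening weight.

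**Conclusion.** The point holds as an inconsistency that should be resolved. Once Screening has passed 10 weeks, no regular visit as scheduled meets 10.1.1, yet 7.1 and the last sentence of footnote b can each point a site away from the visit that 10.1.1 requires. The exposure is narrower under 7.1 (two items, about Days 366-435) than under footnote b read literally (up to four items, depending on the surgery day).

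The number of subjects cannot be derived. About 20 are planned for each surgery window, but the documents do not give the distribution of surgery days within a window.

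The day ranges assume nominal visit timing, and visit windows move the edges by up to 14 days. They also assume that fundus photography counts as an ophthalmic assessment and that the first eye was treated in this study. The Day 42/43 boundary moves with the Screening date; the later ranges do not.

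**What to change.** Reconcile 7.1, 10.1.1 and footnote b, and align the synopsis, into one trigger written per assessment: any item on the 10.1.1 list without a value in the 10-week window is obtained before SE2 surgery, at a regular or an added visit. The passages bearing on which weight enters the second steroid calculation must also be reconciled; that choice belongs to the sponsor.

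In the SAP, report the age of the Period 2 baseline for fundus photographs and vital signs, and flag values outside the 10-week window. Restricting the fundus shift table to in-window baselines would depart from the stated baseline definition, so it should be at most a sensitivity display.

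The cost is protocol wording and one SAP display. Some subjects will need a short extra visit or added items at a regular visit, which 10.1.1 already requires.
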